### 2.2. Background

#### 2.2.1. Glaucoma and Treatment

Glaucoma is a family of diseases commonly characterized by progressive optic neuropathy with associated visual field defects and is the leading cause of irreversible blindness in the world. Glaucoma is classified by Becker-Shaffer into 3 broad types: developmental, angle-closure, and open-angle glaucoma (Stamper 2009). Open-angle glaucoma is further categorized into primary OAG (POAG, sometimes also referred to as chronic OAG) and secondary OAG (which includes pigmentary and pseudoexfoliation glaucoma), with POAG being the predominant form of OAG. POAG is characterized as a multifactorial optic neuropathy with a characteristic acquired atrophy of the optic nerve and loss of ganglion cells and their axons, developing in the presence of open

AC angles, and manifesting characteristic visual field abnormalities ([American Academy of Ophthalmology 2010a](#), [Skuta 2008](#)). Globally, over 60 million people are estimated to be affected by glaucoma (the majority of whom have OAG) and these numbers are expected to increase over time ([Quigley 2006](#), [Varma 2011](#), [Cook 2012](#)). Approximately 10% of eyes with elevated IOP will progress to OAG over the course of a decade ([Quigley 1994](#)).

Although many risk factors have been associated with OAG, elevated IOP remains the most prominent factor and the only factor existing that ophthalmic intervention can reliably affect ([Stamper 2009](#)). A number of controlled trials have demonstrated that lowering IOP will slow or delay the appearance or progression of glaucomatous damage. Large, randomized clinical trials such as the Ocular Hypertension Treatment Study ([Kass 2002](#)) and the Early Manifest Glaucoma Trial ([Heijl 2002](#)) addressed the value of early detection and lowering of elevated IOP in ocular hypertension or POAG. The effects and parameters of various interventions in eyes with established glaucomatous damage were addressed by the Collaborative Initial Glaucoma Treatment Study ([Lichter 2001](#)) and the Advanced Glaucoma Intervention Study ([AGIS 2000](#)).

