### 5.1. Inclusion Criteria

Participants are eligible to be included in the study only if all of the following criteria apply:

1.	Age
1.01	Participant must be at least 18 years of age at the time of signing the informed consent
2.	Sex
2.01	Male or female
3.	Informed Consent
3.01	Written informed consent and authorization for use and release of personal health information are obtained in accordance with the relevant country and local privacy requirements, where applicable (eg, Written Authorization for Use and Release of Health and Research Study Information [US sites] and written Data Protection consent [EU sites])
4.	Contraceptives
4.01	Female participants willing to minimize the risk of inducing pregnancy for the duration of the clinical study and follow-up period
4.02	A female participant is eligible to participate if she is not pregnant (ie, has a negative urine pregnancy result at Baseline; see Appendix 7 ), not breastfeeding, and at least 1 of the following conditions applies: 
 
a. Not a WOCBP as defined in Appendix 7
 
 OR 
 
b. A WOCBP who agrees to follow the contraceptive guidance in Appendix 7 during the study period
 

5.	Other General Criteria
5.01	Participant is willing to withhold his/her IOP treatments in both eyes according to the study requirements, and in the opinion of the investigator, can do so without significant risk  Note: If participants cannot discontinue their currently prescribed therapy in both eyes for up to 6 weeks to meet the Washout period for study entry, the investigator may switch the participant's medication to one that requires a shorter washout interval during the washout of the original medication.
5.02	Participant has the ability to understand and willingness to follow study instructions and is likely to complete all required visits and procedures
5.03	Participant is currently a nonsmoker and has not smoked any nicotine-containing products within the previous 6 months
6.	Ocular Inclusion Criteria
6.01	Diagnosis of either OAG (ie, primary OAG, pseudoexfoliation glaucoma, pigmentary glaucoma) or OHT in the study eye , requiring IOP-lowering treatment

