
2.17
	
Any history of trabeculectomy or other types of glaucoma surgery, including a glaucoma seton or aqueous bypass stents (including MIGS) in the study eye

2.18
	
Any history of intracameral implants or intracameral device administration in the study eye

2.19
	
Peripheral anterior synechiae in the inferior iridocorneal angle on gonioscopic examination at Screening in the study eye

2.20
	
Visual field loss in either eye that, in the opinion of the investigator, is functionally significant (eg, split fixation, field defect within the central 10 degrees that is visually significant or likely to cause central visual impairment upon progression) or shows evidence of progressive visual field loss within the year prior to Baseline
 
Note: The same test methodology should be used for all study-related examinations for a given participant

2.21
	
Evidence of macular edema in either eye during screening or in participant's medical

	history
2.22	Anticipated use of corticosteroids in either eye (except as described in Section 6.5.2) or systemically during the study, or historical use prior to Baseline within: 
 
a. 3 years: intraocular fluocinolone acetonide
 
b. 6 months: intraocular corticosteroid(s) other than fluocinolone; any injectable periocular or sub-Tenon’s/subconjunctival corticosteroid
 
c. 2 months: systemic (eg, oral, intramuscular, intravenous) or topical ocular corticosteroids
 
d. 2 weeks: dermal corticosteroids applied to skin of the eyelid(s), around the eye, or adnexa
 

2.23	Anticipated use of other topical ocular medications in either eye except as described in Section 6.5.2.

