5.4.6.2. Visual Field

Visual field examinations will be assessed by automated perimetry (using either Humphrey 24-2 full threshold program or 24-2 SITA Standard, or Octopus G1 or 24-2 and dynamic or normal strategy) at Screening, Baseline, Month 6, and Month 12/Exit. The same test methodology should be used throughout the entire study for a given participant. Visual field overall results will be recorded on the eCRF as normal or abnormal. Abnormal findings include enlargement of blind spot, superior arcuate scotoma, interior arcuate scotoma, paracentral scotoma, nasal step, central scotoma, generalized depression, and temporal scotoma and other. An eye may exhibit multiple abnormalities. Any post-baseline abnormal findings on visual field will be summarized by eye and by visit regardless of the machine type using number and percentage format to calculate incidences.

In addition, mean deviation or mean defect (MD) and change from baseline will also be recorded in decibels (dB), and will be analyzed by visit by machine type (Humphrey and Octopus respectively). If the machine type is different between baseline and post baseline visit, no change from baseline will be derived. If machine type is missing at post-baseline, but available at baseline, then it will be assumed using same machine type. For participants whose visual field were assessed by one machine type as recorded, the mean deviation or mean defect assessment with missing machine type will be imputed as assessments by the corresponding unique machine type.

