5.4.6.6. Biomicroscopy and Dilated Ophthalmoscopy

Biomicroscopic examinations will be performed for each eye at baseline and post-baseline visits. All findings will be coded using MedDRA dictionary.

Number and percentage of participants with findings showing more than one grade increase in severity from baseline or a positive status change, at 1 or more post-baseline visits, will be presented by coded PT in descending order of incidence rate. For findings that are associated with a severity grade, more than 1 severity grade increase in severity from baseline is defined as a change from no finding to 2 and above, from 0.5 to 2 and above, or from 1 to 3 and above from baseline at any of the follow-up visits. Number and percentage of participants with findings that not associated with a severity grade, a positive status change is defined as a finding present at post-baseline which did not present at baseline will be summarized.

Change from baseline in severity grade for gradable findings and status change from baseline for non-gradable findings will be derived at each post-baseline visits. The method to compare with baseline will be by eye, eye area, finding and MedDRA PT. When conducting comparison from baseline, “Other” is consider as a specific finding itself that is different from findings under any pre-defined terms. If the same PT appears under a pre-defined finding and “Other” within the same eye and eye area, they will be compared with baseline separately.

Dilated ophthalmoscopy including vitreous, macula, retina periphery, lens status and opacification and optic nerve will be performed at Screening, Baseline and Month 12/Exit visits. No severity grade will be assigned for vitreous, retina periphery and macula findings, and summarized together with biomicroscopy findings as non-gradable findings.

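### The visual-field findings table sets no baseline condition, so as written it gives prevalence by visit under the name of incidence

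*SAP*

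**What the plan says.** SAP 5.4.6.2 schedules visual fields "at Screening, Baseline, Month 6, and Month 12/Exit". On recording it states: "Visual field overall results will be recorded on the eCRF as normal or abnormal". An abnormal field also carries one or more named findings, such as a type of scotoma or a nasal step. Two analyses follow.

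- **Findings.** "Any post-baseline abnormal findings on visual field will be summarized by eye and by visit regardless of the machine type". The SAP says that this will be done "using number and percentage format to calculate incidences". No condition on baseline status, baseline column or shift table is described.
- **MD.** Mean deviation or mean defect in decibels, with change from baseline, by visit and by machine type.

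SAP 5.4 defines the baseline value for safety parameters but does not limit any table to new findings.

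For non-gradable biomicroscopy and dilated ophthalmoscopy findings, SAP 5.4.6.6 does set a baseline condition: "a positive status change is defined as a finding present at post-baseline which did not present at baseline".

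On eligibility, Protocol 5.1 (criterion 6.01) admits "Diagnosis of either OAG (ie, primary OAG, pseudoexfoliation glaucoma, pigmentary glaucoma) or OHT". Protocol 5.2 (criterion 2.20) excludes field loss that, in the investigator's opinion, "is functionally significant (eg, split fixation, field defect within the central 10 degrees" and similar, or that has progressed in the year before Baseline.

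**The concern.** An incidence counts eyes that acquire a finding during follow-up. The rule in SAP 5.4.6.2 counts eyes that have a finding at a follow-up visit, whether or not it was there before treatment. The two agree only if no eye has a field defect at entry, and the eligibility criteria do not ensure that.

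Visual field is one of the safety measures named in Protocol Section 3 and SAP 1.1. If the percentages are read as their label suggests, stable glaucomatous defects will look like events on treatment, and a small number of new defects will be hard to pick out among them.

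**Working it through.** The documents state no visual-field rate, so there is no figure to reproduce. The check compares the texts and then illustrates the size.

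**Step 1. Can eyes have a defect at baseline?** Yes. OAG is eligible under criterion 6.01. Protocol 2.2.1 describes primary OAG as "manifesting characteristic visual field abnormalities"; that is background text on one form of OAG, but it shows that defects are expected in part of this population. Criterion 2.20 leaves in defects that are stable and not functionally significant. Ocular hypertension is also eligible, and those eyes may have normal fields.

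**Step 2. Does the counting rule remove them?** No. The rule covers any post-baseline abnormal finding. A stable nasal step present at Baseline satisfies it at Month 6 and at Month 12. Under the rule of SAP 5.4.6.6, the same kind of carry-over would not count.

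**Step 3. How far apart can the two figures be?** Let b be the share of eyes abnormal at baseline and p the share of baseline-normal eyes that become abnormal. Assume that baseline defects persist. For an any-abnormality row:

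- as written: b + (1 − b)p
- new abnormality among baseline-normal eyes: p
- share of counted eyes already abnormal at baseline: b / [b + (1 − b)p]

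Both b and p are assumptions (b = 20%, 40%, 60%; p = 0%, 5%, 10%). Counts use 30 study eyes, the upper end of the 25 to 30 planned for the Bimatoprost SR cohort (SAP Section 3).

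| b | p | As written | Eyes counted of 30 | Newly abnormal eyes | Already abnormal among those counted |
|---|---|---|---|---|---|
| 20% | 0% | 20% | 6.0 | 0.0 | 100% |
| 20% | 5% | 24% | 7.2 | 1.2 | 83% |
| 20% | 10% | 28% | 8.4 | 2.4 | 71% |
| 40% | 0% | 40% | 12.0 | 0.0 | 100% |
| 40% | 5% | 43% | 12.9 | 0.9 | 93% |
| 40% | 10% | 46% | 13.8 | 1.8 | 87% |
| 60% | 0% | 60% | 18.0 | 0.0 | 100% |
| 60% | 5% | 62% | 18.6 | 0.6 | 97% |
| 60% | 10% | 64% | 19.2 | 1.2 | 94% |

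Example: b = 0.6 and p = 0.1 give 0.6 + 0.4 × 0.1 = 0.64, that is 19.2 of 30 eyes, of which 0.4 × 0.1 × 30 = 1.2 are new.

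With no new loss at all, the row still reads 20% to 60%.

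**Step 4. Limits of the illustration.** It describes a single row for any abnormality. The SAP lists separate finding types, and the carry-over for one type depends on how common that type is at baseline, which can be well below b. The comparator p applies only to eyes normal at baseline; over all eyes, the newly abnormal share is (1 − b)p. The formula also leaves out new findings in eyes that already have another defect.

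**The case against.** **The SAP does not say that baseline defects are counted.** The word incidences may have been meant to restrict the table to new findings. This stands as a point about intent: a reader might infer that the sponsor chose to count existing defects, and the documents do not show that. The instruction itself, however, covers any post-baseline finding, and a programmer following it would include them.

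**New field loss is not left unexamined.** A reader might infer that a true signal would be lost. The documents do not support that.

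- MD change from baseline is analyzed in the same section, and the requirement to keep one test methodology per participant protects within-participant change.
- Ocular results are listed by participant (SAP 5.4 and 6.3.2). With about 35 participants, each eye can be followed by hand.
- Treatment-emergent ocular adverse events are tabulated by eye (SAP 5.4.2). This cover is partial, because Protocol Appendix 3 keeps expected progression of the study disease out of the adverse events unless it is more severe than expected.

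What remains is that none of these summarizes new focal defects, and a listing does not correct a mislabelled percentage.

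**The rule in 5.4.6.6 is not uniform across the SAP.** Hyperemia is shown as worst severity observed, with a separate summary of worsening (5.4.6.3); lens opacity is shown as presence and severity by visit (5.4.6.6.2); synechiae are listed if seen at any time (5.4.6.7). Showing observed findings is therefore legitimate in itself. The difficulty is calling the result an incidence without a baseline reference.

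**Study eye against fellow eye.** A reader might also infer that these rows would differ mainly because of disease burden at entry. Burden could differ, since only one eye need qualify, but when both qualify the study eye is chosen on IOP, not on field status (Protocol Section 5). The documents give no basis for calling it the main cause.

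**Conclusion.** The point holds for the findings table in SAP 5.4.6.2. As written, it yields the prevalence of field abnormalities by visit, labelled as incidence. This rests on three things in the text: the rule covers any finding, it sets no baseline condition, and eyes with stable defects are eligible.

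The size is unknown, because the documents do not give the share of eyes abnormal at baseline. Under the assumed ranges, an any-abnormality row reads 20% to 64% against 0% to 10% among baseline-normal eyes, and 71% to 100% of the counted eyes were abnormal already. These figures are illustrative and do not forecast this trial. It would also go too far to say that the table measures how common glaucoma is: eyes with ocular hypertension may have normal fields, and a listed finding need not be glaucomatous.

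The consequence is limited to one descriptive safety table in a study without hypotheses. The primary and secondary efficacy analyses and the sample size are not affected. A correction is still worthwhile because visual field is a named safety measure and the data needed are already collected.

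**What to change.** In SAP 5.4.6.2:

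1. Count findings that are present after baseline and were absent at baseline in the same eye, by finding type, following the approach of SAP 5.4.6.6.
2. Use as denominator, for each finding type, the eyes that lack that finding at baseline and have a post-baseline field.
3. Add a shift table of normal or abnormal at baseline against normal or abnormal at each visit, by eye.
4. If the table of all findings is kept, add a baseline column and label it prevalence.
5. Keep the MD change analysis. Counting only new findings does not show an existing defect getting worse, and neither does the shift table in an eye that is already abnormal.

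The cost is SAP wording, one derivation and one added table. Screening and Baseline fields are already scheduled, so no new data and no protocol change are needed.

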5.4.6.3. Macroscopic Conjunctival Hyperemia

Macroscopic conjunctival hyperemia assessment will be performed at all scheduled visits except on the administration day. Conjunctival hyperemia severity is assessed as 0 (None), +0.5 (Trace), +1 (Mild), +2 (Moderate), +3 (Severe) or 'Not Evaluable.' These data will be summarized overall by treatment cohort and associated eye using the worst severity of hyperemia observed.

In addition, worst severity grade increases greater than 1 (worsening ie, a change from 0 to 2 and above, from 0.5 to 2 and above, or from 1 to 3 and above) in hyperemia from baseline will also be summarized overall and by treatment cohort. If the worst severity grade during a period is less severe compared to baseline, it will be considered as 'no increase.'

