
2.09
	
Any history of external ocular or intraocular malignancy, and/or any history of benign ocular neoplasia in the study eye that in the investigator’s opinion resulted in clinically significant ocular morbidity

2.10
	
History of herpetic ocular diseases in the study eye (including herpes simplex virus and varicella zoster virus)

2.11
	
Active ocular surface findings other than bulbar conjunctival hyperemia, on either macroscopic or slit-lamp examination, > +1 (mild) at Baseline in the study eye

2.12
	
The anticipated wearing of contact lenses in the study eye during the study that deviates from the following (contact lens wear is allowed during the study, but is to be temporarily discontinued before study visits, and before and after Bimatoprost SR administration according to the following):
 
 
a. Use of soft lenses should be discontinued at least 3 days prior to Baseline, and use of rigid gas permeable or hard contact lenses should be discontinued at least 1 week prior to Baseline
 
b. Use of soft lenses should be discontinued at least 3 days and use of rigid gas permeable or hard contact lenses should be discontinued at least 1 week prior to a scheduled study visit or Bimatoprost SR administration visit
 
c. Use of contact lenses of any kind should be discontinued for 1 week following any Bimatoprost SR administration
 
d. Use of contact lenses of any kind from 08:00 ± 30 minutes through completion of last IOP measurement of Sleep Lab visits ending at 06:00 ± 30 minutes
 

2.13
	
Central corneal thickness of < 480 or > 620 micrometers in the study eye

2.14
	
Anticipated need for any incisional or laser ocular surgery in the study eye during the study

2.15
	
History of anatomically narrow angle resulting in evidence of angle changes, and/or any history of acute angle closure glaucoma, in the study eye
 
Note: historically narrow-angled participants who have not experienced an acute attack of angle closure and whose angle has been opened by cataract surgery or peripheral iridotomy may be eligible for enrollment if they have no evidence of angle abnormalities

2.16
	
History or evidence of a peripheral iridotomy/iridectomy in the inferior iris in the study eye

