4.1. Safety Analysis Set (SAF)

All participants who have received study intervention (ie, Bimatoprost SR administration or LUMIGAN 0.01%) will contribute to the SAF. All safety data collected from these participants will be included in the SAF.

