5.1.1. Statistical Notation and Presentation

Continuous variables will be summarized by cohort (Bimatoprost SR or LUMIGAN 0.01%) for number of participants, mean, standard deviation (SD), median, first quartile, third quartile, minimum, and maximum values. Categorical variables will be summarized by frequency counts and percentage of participants within each treatment cohort.

All statistical analyses will be performed using Statistical Analysis Software (SAS®) version 9.4.

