5.4. Safety Analysis

Descriptive statistics will be used to summarize the safety data by cohorts based on the SAF. The safety parameters will include the following non-ocular safety parameters: non-ocular AEs and vital signs; ocular safety parameters: visual field examination, visual acuity, macroscopic conjunctival hyperemia assessment, biomicroscopy, dilated ophthalmoscopy (including optic disc assessment), pachymetry, gonioscopy (including angle assessment), and specular microscopy. Results from ocular safety assessments will be summarized by participants and listed, including scheduled and unscheduled assessments (if any). The results will be presented by treatment cohorts for the study eye and pooled treatment cohorts for the fellow eye. Unless

otherwise stated, the last nonmissing safety assessment before the first dose of study treatment will be used as the baseline for all analyses of that safety parameter.

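### If any eye enters with moderate or severe conjunctival hyperemia, the SAP's only change-from-baseline hyperemia summary cannot show it worsening, yet keeps it in the denominator

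*SAP*

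**What the plan says.** **Entry.** Protocol 5.2, exclusion 2.11, bars study eyes with surface findings above +1 at Baseline but carves out one finding: "Active ocular surface findings other than bulbar conjunctival hyperemia, on either macroscopic or slit-lamp examination". The criterion does not cover the fellow eye.

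**Scale.** SAP 5.4.6.3: "Conjunctival hyperemia severity is assessed as 0 (None), +0.5 (Trace), +1 (Mild), +2 (Moderate), +3 (Severe"), plus a not-evaluable category.

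**Summaries.** The same section plans two. One gives the worst grade observed, by cohort and eye. The other covers "worst severity grade increases greater than 1", defined as "a change from 0 to 2 and above, from 0.5 to 2 and above, or from 1 to 3 and above". Eyes that improve are retained: "If the worst severity grade during a period is less severe compared to baseline, it will be considered as" no increase.

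**Denominator.** SAP 5.4.6.3 states none, so the general text governs:
- SAP 5.4: "Descriptive statistics will be used to summarize the safety data by cohorts based on the SAF"
- SAP 4.1, on treated participants: "All safety data collected from these participants will be included in the SAF"
- SAP 5.1.1: "Categorical variables will be summarized by frequency counts and percentage of participants within each treatment cohort"

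SAP 5.4 adds that ocular results are shown by cohort for the study eye and pooled across cohorts for the fellow eye.

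**The concern.** Macroscopic bulbar conjunctival hyperemia is a named safety measure in Protocol 3 and SAP 1.1. The protocol chose not to cap it at entry, but the one planned summary of its change from baseline works only for eyes that start at +1 or lower. For an eye starting higher, the table returns no increase whatever happens on study, including a move from moderate to severe.

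The worst-grade summary does not fill this gap. An eye at +3 throughout and an eye that goes from 0 to +3 look the same in it. At stake is whether a reader of the tables can tell how much hyperemia arose or worsened on treatment, and over which eyes the worsening percentage was taken.

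**Working it through.** **Inputs.** The grades (0, 0.5, 1, 2, 3) and the threshold (rise greater than 1) come from SAP 5.4.6.3. The cohort sizes (25 to 30 Bimatoprost SR, 5 LUMIGAN 0.01%) come from SAP 3. The number k of eyes with baseline grade 2 or 3 and the number x of eyes meeting the rule are not given; the values below are assumptions.

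**Step 1: reproduce the SAP's list.** Of the 5 x 5 = 25 pairs of baseline and post-baseline grade, those with post minus baseline above 1 are 0 to 2, 0 to 3, 0.5 to 2, 0.5 to 3 and 1 to 3. These are exactly the five transitions the SAP lists. Counting more than one step along the scale would add 0 to 1, which the SAP does not list. The rule is therefore a numeric difference.

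**Step 2: the ceiling.** The largest possible rise is 3 minus baseline:
- from +2: 3 - 2 = 1, which is not greater than 1
- from +3: 3 - 3 = 0

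None of the five qualifying pairs starts at +2 or +3, and none would under the step-counting reading either.

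**Step 3: effect on the percentage.** Because the k eyes cannot qualify, all x events come from the other N - k.

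Reported = x/N. Among eyes able to meet the rule = x/(N - k). Ratio = (N - k)/N.

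| N | k (assumed) | x (assumed) | Reported | Among eyes at +1 or less | Ratio |
|---|---|---|---|---|---|
| any | 0 | any | x/N | x/N | 1.000 |
| 30 | 1 | 6 | 20.0% | 6/29 = 20.7% | 0.967 |
| 30 | 3 | 6 | 20.0% | 6/27 = 22.2% | 0.900 |
| 30 | 5 | 6 | 20.0% | 6/25 = 24.0% | 0.833 |
| 25 | 1 | 5 | 20.0% | 5/24 = 20.8% | 0.960 |
| 5 | 1 | 1 | 20.0% | 1/4 = 25.0% | 0.800 |

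The ratio depends only on k and N; x merely sets the level.

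**Step 4: where else a +2 to +3 change would show.**
- Listings: SAP 5.4 and 6.3.2 list all scheduled and unscheduled assessments.
- Worst-grade table: the eye appears as severe, without its baseline.
- Adverse events: Protocol Appendix 3 accepts exacerbation of a pre-existing condition as an AE, and SAP 5.4.2 treats worsening after treatment start as treatment-emergent. This depends on the investigator reporting it.

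**The case against.** **Such eyes may be few or absent.** This stands. Protocol Table 6-2 requires at least 28 days' washout of prostaglandin-type drops, exclusion 2.08 lets the investigator exclude active study-eye disease, and 2.12 stops contact lens wear before Baseline. A reader might infer that worsening is understated as a matter of fact. The documents support that only if at least one eye enters at +2 or +3, and they do not say that any will.

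**The change is not lost.** This stands too. A reader might infer that every +2 to +3 change disappears from the report. Step 4 shows otherwise, and with about 35 participants the listing can be read directly. What is missing is a table showing it as a change.

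**The threshold is deliberate.** Agreed. A +1 to +2 change is not counted either, and SAP 5.4.6.6 applies the same rule to graded biomicroscopy findings. Counting +2 to +3 as an event while leaving out +1 to +2 would be inconsistent. The point is the ceiling, not the choice of threshold.

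**The safety-set percentage is a valid statistic.** It is: it gives the share of all treated participants with a qualifying rise. The rate among eyes able to qualify answers a different question. This argues for showing both. The denominator is also inferred from general text, though nothing in the SAP points to another.

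**Fellow eyes are not wholly unrestricted.** Correct. Exclusions 1.04 and 2.07 leave room for judgement on conditions that could confound results. Only a numeric grade limit is absent.

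**Conclusion.** The point holds conditionally. Entry at +2 or +3 is permitted, such an eye cannot meet the rule, and the general denominator rules retain it. If one enters, the only planned change-from-baseline hyperemia summary cannot show it going from moderate to severe, and the reported percentage falls below the rate among eyes able to meet the rule by the factor (N - k)/N. One eye of 30 gives 0.967; one of 5 gives 0.80, which in a cohort that small describes a single participant. The true size is unknown and may be zero.

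The conclusion rests on reading SAP 4.1, 5.1.1 and 5.4 as setting the denominator for 5.4.6.3. The consequence is small: the study has no hypotheses, the summary is descriptive, and no primary or secondary endpoint is touched. It merits a cheap improvement to one safety display.

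**What to change.** In SAP 5.4.6.3:

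1. Add a table of baseline grade by worst post-baseline grade, for the study eye by cohort and for the fellow eye pooled. It handles the ceiling for any k and shows what k is.
2. Keep the existing summary of rises greater than 1 on the safety set. Beside it, give the number of eyes with baseline grade +1 or less and the percentage among them.
3. Show any +2 to +3 change in a separate row, not merged into the greater-than-1 count.

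The grades are already collected at the Baseline Office visit and later visits, so no new data are needed. The cost is one small table and a sentence defining the second denominator. The added rate may look slightly less favourable than the one now planned.
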